8.5 Analysis Populations

8.5.1 Safety Analysis Population

The safety population will be used for the analysis of safety data in this study. The safety population consists of all subjects who received at least 1 stimulation protocol of trial treatment. Subjects will be included in the treatment group corresponding to the trial treatment they received for the analysis of safety data using the safety population. Subjects who take incorrect trial treatment for the entire treatment period will be included in the treatment group corresponding to the trial treatment received.

At least 1 vital sign measurement obtained after at least 1 stimulation protocol of trial treatment is required for inclusion in the analysis of each specific parameter. To assess change from baseline, a baseline measurement is also required.

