4.2.2.1 Rationale for the Use of Sham

In order to assess the efficacy of the therapy in clinical outcomes, comparison between active and sham treatment is required. Using sham or placebo for 6 months is accepted for patients with ALS as shown in the most recent phase 2 and 3 trials. In order to encourage participation and fulfill patients' expectations, sham treated patients will receive active stimulation during the open label extension period (OLE), intended to collect more safety data and to assess sustainability of the efficacy observed in the double-blinded period (DBP).

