7.1.5.1.2 Visit 2: baseline

Patients will be randomized to either treatment or sham stimulation and assigned a code (except for patient sin stage 1, which are not randomized, and all receive active stimulation). Before starting stimulation, the researcher will conduct a vital signs, physical exam and neurological examination. Urine (50 ml) and blood (20 ml) will be collected and stored. Then, the patient will be subjected to the first TPS stimulations (a 20 min stimulations).

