8.6 Statistical Methods

Safety and tolerability will be assessed by statistical and clinical review of the following data collected throughout the study: adverse experiences (AEs), and treatment-emergent suicidality derived from the C-SSRS. Safety will be evaluated with doses combined; selected safety analyses will be performed for doses separately.

The analysis of safety results will follow a tiered approach ([Table 6](#)). The tiers differ with respect to the analyses that will be performed. Safety parameters or adverse experiences of special interest that are identified *a priori* constitute “Tier 1” safety endpoints that will be subject to inferential testing for statistical significance with p-values and 95% confidence intervals provided for between-group comparisons. Other safety parameters will be considered as Tier 2 or Tier 3. Tier 2 parameters will be assessed via point estimates with 95% confidence intervals provided for between-group comparisons.

Membership in Tier 1 requires that at least 4 subjects in any treatment group exhibit the event; all other adverse experiences and predefined limits of change will belong to Tier 2.

Summary statistics for baseline, on-treatment, and change from baseline values will be provided by the treatment group in table format.

See [Table 6](#) for a classification of safety endpoints as Tier 1, or 2 and the corresponding analysis strategy for each endpoint.

Table 6 Analysis Strategy for Safety Parameters

Safety Tier	Safety Endpoint [†]	p-Value [§]	95% CI for Treatment Comparison [§]	Descriptive Statistics
Tier 1	Any AE		X	X

	Any Serious AE Any Drug-Related AE Any Serious and Drug-Related AE Discontinuation due to AE Specific AEs, SOCs, or PDLCs (incidence ≥ 4 subjects in 1 of the treatment groups)		X X X X X X X X X X
Tier 2	Specific AEs, SOCs or PDLCs [‡] (incidence <4 subjects in all the treatment groups) Change from Baseline Results (ECGs, Vital Signs)		X X
² Adverse Event (AE) references refer to both Clinical and Laboratory AEs.			
³ Includes only those endpoints not pre-specified as Tier 1 or not already pre-specified as Tier-2 endpoint			
⁴ P-value and CI for safety endpoints based upon Miettinen & Nurminen method			
Note: SOC=System Organ Class; PDLC=Pre-Defined Limit of Change; X = results will be provided.			

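### As written, the TPS-versus-sham safety comparison takes in the 10 non-randomised Stage 1 patients, and the protocol gives it two conflicting time windows

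*Protocol*

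**What the plan says.** Protocol 8.5.1 defines a single safety population: "The safety population consists of all subjects who received at least 1 stimulation protocol of trial treatment". It groups by exposure: "Subjects will be included in the treatment group corresponding to the trial treatment they received". The only special case it adds is a subject given the wrong treatment for the whole treatment period.

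Sections 8.4.2 and 8.6 both base the safety assessment on "statistical and clinical review of the following data collected throughout the study". Section 8.6 then makes Tier 1 events subject to "inferential testing for statistical significance with p-values and 95% confidence intervals provided for between-group comparisons", and gives Tier 2 parameters confidence intervals between groups. The method named under Table 6 is Miettinen and Nurminen. No stratification by stage is mentioned.

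Two design features matter here. Section 7.1.5.1.2 describes Stage 1 patients as ones "which are not randomized, and all receive active stimulation". For Stage 2, section 4.2.2.1 says that "sham treated patients will receive active stimulation during the open label extension period (OLE", which follows the double-blind period (DBP).

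Two statements pull the other way. Section 8.4.2 names Visit 2 as the primary time for safety. Section 8.1 says that results will be descriptive only, and Table 5 gives descriptive statistics as the method for key safety analyses.

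**The concern.** The Stage 2 double-blind period is the only controlled safety evidence in this trial, and section 3.4 states a hypothesis that TPS is safe and well tolerated. Someone programming the tables from sections 8.5.1 and 8.6 would put Stage 1 patients in the TPS column. They meet the population definition and received only TPS. They were not randomised, knew they were on active treatment, were enrolled earlier and were followed for less time. Differences between the columns would then mix treatment with stage, blinding and length of follow-up.

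The window raises a second problem. If all study data count, a sham patient who enters the extension has received both treatments, and grouping by treatment received no longer places that patient. If Visit 2 governs, the extension is out, but so is almost all of the blinded treatment. The analyst would have to choose after the fact.

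**Working it through.** The protocol states no figure for the safety comparison, so there is none to reproduce. It also gives no adverse event rates. All risks below are assumptions.

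**Inputs from the protocol**
- Stage 1 n = 10, Stage 2 n = 40 (8.9).
- Stage 2 allocation is 2:1 in section 1.0 and 1:1 in section 5.3, so about 27 and 13, or 20 and 20. Both are shown.
- Follow-up: Stage 1 to week 8 (3.1), or week 4 in the flow chart (6.0). DBP 6 months (1.0), or week 16 in the flow chart. Extension 6 months (1.0), or weeks 16 to 34 in the flow chart.
- Sessions: 6 in 2 weeks, then single sessions at months 2 and 4 (5.2.1, 5.2.2).

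**Step 1. Who is in each column**
- 2:1: TPS 27 + 10 = 37, sham 13. Stage 1 share 10/37 = 27%.
- 1:1: TPS 20 + 10 = 30, sham 20. Stage 1 share 10/30 = 33%.

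Stage 1 patients also have a Visit 2, so the Visit 2 rule does not remove them.

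**Step 2. Pooling Stage 1 when risk follows time, no true effect**

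Assume a constant hazard, equal in both arms, and a 24-week risk p. The 8-week risk is 1 - (1 - p)^(8/24). For p = 40% it is 1 - 0.6^(1/3) = 15.7%.
- 2:1: (10 × 0.157 + 27 × 0.40)/37 = 33.4%, against 40% on sham: -6.6 points.
- 1:1: (10 × 0.157 + 20 × 0.40)/30 = 31.9%, against 40%: -8.1 points.

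| 24-week risk | Shift, 2:1 | Shift, 1:1 |
|---|---|---|
| 20% | -3.5 | -4.3 |
| 40% | -6.6 | -8.1 |
| 60% | -9.1 | -11.2 |
| 80% | -10.4 | -12.8 |

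The exact rejection rate of the unstratified Miettinen-Nurminen test at two-sided 0.05 is 4.8% to 5.0% for randomised DBP data alone. With Stage 1 pooled it is 6.1% to 8.0% (2:1) or 6.2% to 14.1% (1:1). With the flow chart's weeks (4 and 16) and 16-week risks of 20% to 60%, the shift is -3.9 to -13.2 points.

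**Step 3. Pooling Stage 1 for stimulation-linked events**

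Sections 4.1.2 and 4.1.3 describe headache and fatigue that clear in 24 to 48 hours. Assume a headache risk of 30% on TPS and 10% on sham over the DBP, a true difference of 20 points. If risk follows sessions and Stage 1 patients receive 6 of the 8, their risk is 1 - 0.7^(6/8) = 23.5%.
- 1:1: (10 × 0.235 + 20 × 0.30)/30 = 27.8%, difference 17.8 points.
- 2:1: (10 × 0.235 + 27 × 0.30)/37 = 28.2%, difference 18.2 points.

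The dilution is about 2 points. If the same risk were spread evenly over 26 weeks, the 8-week risk would be 1 - 0.7^(8/26) = 10.4%, the differences 13.5 (1:1) and 14.7 (2:1), and the dilution 6.5 and 5.3 points.

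**Step 4. Letting the extension in**

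Take Step 2 again, and count all extension exposure as TPS while sham patients also keep their sham DBP record. For p = 40% the 48-week risk is 1 - 0.6² = 64%.
- 2:1: (10 × 0.157 + 27 × 0.64 + 13 × 0.40)/50 = 48.1%, which is +8.1 points.
- 1:1: (10 × 0.157 + 20 × 0.64 + 20 × 0.40)/50 = 44.7%, which is +4.7 points.

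Over risks of 20% to 80% the range is +0.9 to +8.1 (2:1) and -1.3 to +4.7 (1:1).

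If extension events instead stay with the original arm and both arms continue, the 30% and 10% example becomes 1 - 0.7 × 0.7 = 51% against 1 - 0.9 × 0.7 = 37%, a difference of 14 points rather than 20.

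**Step 5. What Visit 2 covers**

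Section 7.1.5.1.2 places the first stimulation at Visit 2, which is 1 of 8 blinded sessions. Section 7.1.4.1 speaks of three planned stimulations during Visit 2. On either account most sessions and nearly all blinded follow-up fall outside it.

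**The case against.** The strongest reply is that the protocol nowhere orders pooling. It keeps the stages apart in design, objectives and endpoints, Stage 1 has no comparator, and tables by stage and period are commonly left to a separate SAP. This stands in part: pooling follows from the missing restriction, not from an instruction. But section 8.0 is itself titled as the statistical analysis plan, and it already fixes the population, the grouping rule, the data source and the test. Followed as written, these put Stage 1 in the TPS column.

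The reply on the extension is stronger. Visit 2 is the only specific analysis time stated and it precedes the extension, so extension data need not enter the primary comparison. At Visit 2 the unequal follow-up of Stage 1 also disappears. Both points stand. They do not restore randomisation, and they leave the Visit 2 rule in conflict with the whole-study data source.

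A reader might infer that crossed-over sham patients must be counted under sham, that TPS would therefore look safer than it is, or even that a true excess would reverse in sign. The documents do not support this. Grouping after crossover is undefined, and attribution by treatment at the time of the event is equally open. A reversal in the 30% and 10% example (30% against 37%, or -7 points) needs only sham patients to continue. Section 4.2.2.1 gives the extension the further purpose of assessing whether efficacy is sustained, which points to active patients continuing too.

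Finally, the descriptive-only statements in 8.1 and Table 5 lower the stakes if they govern. They contradict the testing in 8.6, and by-group tables would carry the same mixture.

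**Conclusion.** The point holds as a fault in the stated rules, of moderate weight. Stage 1 patients fall into the TPS group, as 27% or 33% of it, and the comparison with sham is then not a randomised one. The safety window is contradictory, and neither version yields a usable comparison over the double-blind period.

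The size is uncertain because every event risk is assumed. Pooling Stage 1 alone shifts the difference by about -3.5 to -12.8 points with no true effect, if hazard is constant over time and follow-up is 8 against 24 weeks. For stimulation-linked events the dilution is about 2 points, if risk follows sessions and Stage 1 receives 6 of 8. Once extension data enter, even the sign depends on attribution. It is therefore not established that TPS would look safer overall. What is established is that the result would depend on choices the protocol leaves open or states in two ways.

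**What to change.** In 8.4.2, 8.5.1 and 8.6:
- Limit every TPS-versus-sham safety comparison (tests, confidence intervals or by-group tables) to randomised Stage 2 subjects.
- Count events from the first blinded stimulation to the earlier of the end-of-DBP visit and the first extension stimulation, grouped by treatment received in the DBP. Replace the Visit 2 primary time with this window.
- Report Stage 1 separately.
- Report extension events separately, all as on active TPS, split by original arm.
- Reconcile the descriptive-only statements in 8.1 and Table 5 with the testing in 8.6.

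The cost is wording and one extra set of tables, with no new data. The TPS column of the comparison falls from 37 to 27 (2:1) or from 30 to 20 (1:1), with some loss of precision.

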8.6 Statistical Methods

Safety and tolerability will be assessed by statistical and clinical review of the following data collected throughout the study: adverse experiences (AEs), and treatment-emergent suicidality derived from the C-SSRS. Safety will be evaluated with doses combined; selected safety analyses will be performed for doses separately.

The analysis of safety results will follow a tiered approach ([Table 6](#)). The tiers differ with respect to the analyses that will be performed. Safety parameters or adverse experiences of special interest that are identified *a priori* constitute “Tier 1” safety endpoints that will be subject to inferential testing for statistical significance with p-values and 95% confidence intervals provided for between-group comparisons. Other safety parameters will be considered as Tier 2 or Tier 3. Tier 2 parameters will be assessed via point estimates with 95% confidence intervals provided for between-group comparisons.

Membership in Tier 1 requires that at least 4 subjects in any treatment group exhibit the event; all other adverse experiences and predefined limits of change will belong to Tier 2.

Summary statistics for baseline, on-treatment, and change from baseline values will be provided by the treatment group in table format.

See [Table 6](#) for a classification of safety endpoints as Tier 1, or 2 and the corresponding analysis strategy for each endpoint.

Table 6 Analysis Strategy for Safety Parameters

Safety Tier	Safety Endpoint [†]	p-Value [§]	95% CI for Treatment Comparison [§]	Descriptive Statistics
Tier 1	Any AE		X	X

	Any Serious AE Any Drug-Related AE Any Serious and Drug-Related AE Discontinuation due to AE Specific AEs, SOCs, or PDLCs (incidence ≥ 4 subjects in 1 of the treatment groups)		X X X X X X X X X X
Tier 2	Specific AEs, SOCs or PDLCs [‡] (incidence <4 subjects in all the treatment groups) Change from Baseline Results (ECGs, Vital Signs)		X X
² Adverse Event (AE) references refer to both Clinical and Laboratory AEs.			
³ Includes only those endpoints not pre-specified as Tier 1 or not already pre-specified as Tier-2 endpoint			
⁴ P-value and CI for safety endpoints based upon Miettinen & Nurminen method			
Note: SOC=System Organ Class; PDLC=Pre-Defined Limit of Change; X = results will be provided.			

8.6.3 Summaries of Baseline Characteristics, Demographics, and Other Analyses

8.6.3.1 Demographic and Baseline Characteristics

Demographic variables (e.g., age, gender, race), baseline characteristics, primary and secondary diagnoses, and prior and concomitant therapies will be summarized by treatment either by descriptive statistics or categorical tables.

8.7 Interim Analysis

No interim analyses for efficacy or safety are planned for this study

8.8 Multiplicity

Not planned.

8.9 Sample Size and Power Calculations

Sample size

This study will recruit 10 patients for stage 1 (open label) and 40 patients for stage 2 (randomized DBP). Using the results from the CENTAUR trial¹ in patients with ALS, a sample size of 6 patients per arm provided a 90% to detect differences by week 24 with alpha 0.05.

Power for the primary hypothesis

Considering that this is a pilot study, and no previous data is available for this intervention, a convenience sample size of 10 subjects for stage 1 and 40 for stage 2 has been defined. Using the results from the CENTAUR trial¹ in patients with ALS, a sample size of 6 patients per arm provided a 90% to detect differences by week 24 with alpha 0.05.

8.10 Subgroup Analyses

NA

8.11 Compliance (Treatment Adherence)

Summary statistics will be provided on percent compliance by treatment for all subjects included.

8.12 Extent of Exposure

The total number of days each subject received a particular total daily stimulation protocol will be identified and then summarized (as subject counts and percentages)

9.0 LABELING, PACKAGING, STORAGE AND RETURN OF CLINICAL SUPPLIES

No drugs are being tested in this study

10.1.4 Confidentiality of Ethics Committee Information

The principal investigator is required to record the name and address of the Ethics Committee that reviews and approves this trial.

10.2 Compliance with Financial Disclosure Requirements

The investigator/subinvestigator(s) agree to provide his/her financial interests to allow for the submission of complete and accurate certification and disclosure statements. The investigator/subinvestigator(s) further agree to provide this information on a Certification/Disclosure Form, commonly known as a financial disclosure form.

10.3 Compliance with Law, Audit and Debarment

By signing this protocol, the investigator agrees to conduct the trial in an efficient and diligent manner and in conformance with this protocol; generally accepted standards of Good Clinical Practice (e.g., International Conference on Harmonization (ICH) of Technical Requirements for Registration of Pharmaceuticals for Human Use Good Clinical Practice: all applicable federal, state, and local laws, rules and regulations relating to the conduct of the clinical trial.

The Code of Conduct, a collection of goals and considerations that govern the ethical and scientific conduct of clinical investigations, is provided in Section 12.1 Hospital del Mar Neurosciences Code of Conduct for Clinical Trials.

The investigator also agrees to allow monitoring, audits, Ethics Committee review and regulatory authority inspection of trial-related documents and procedures and provide for direct access to all trial-related source data and documents.

The investigator agrees not to seek reimbursement from subjects, their insurance providers or from government programs for procedures included as part of the trial reimbursed to the investigator.

The investigator shall prepare and maintain complete and accurate trial documentation in compliance with Good Clinical Practice standards and applicable federal, state, and local laws, rules, and regulations; and, for each subject participating in the trial, provide all data, and, upon completion or termination of the clinical trial, submit any other reports to the regulatory agencies.

Trial documentation will be promptly and fully disclosed by the investigator upon request and shall be made available at the trial site upon request for inspection, copying, review and audit at reasonable times from any regulatory authorities. The investigator agrees to promptly take any reasonable steps that are requested because of an audit to cure deficiencies in the trial documentation and worksheets/case report forms.

The investigator must maintain copies of all documentation and records relating to the conduct of the trial in compliance with all applicable legal and regulatory requirements. This documentation includes, but is not limited to, the protocol, worksheets/case report forms, advertising for subject participation, adverse event reports, subject source data,

correspondence with regulatory authorities, consent forms, investigator's curricula vitae, monitor visit logs, laboratory reference ranges, laboratory certification or quality control procedures and laboratory director curriculum vitae. By signing this protocol, the investigator agrees that documentation shall be retained until at least 2 years after the last approval of a marketing application in an ICH region or until there are no pending or contemplated marketing applications in an ICH region or until at least 2 years have elapsed since the formal discontinuation of clinical development of the investigational product. Because the clinical development and marketing application process is variable, it is anticipated that the retention period can be up to 15 years or longer after protocol database lock. All trial documents shall be made available if required by relevant regulatory authorities. The investigator must consult with and obtain written approval prior to destroying trial and/or subject files.

ICH Good Clinical Practice guidelines recommend that the investigator inform the subject's primary physician about the subject's participation in the trial if the subject has a primary physician and if the subject agrees to the primary physician being informed.

10.4 Compliance with Trial Registration and Results Posting Requirements

The principal investigator of the trial is solely responsible for determining whether the trial and its results are subject to the requirements for submission to EUDRA (<http://eudragmdp.ema.europa.eu>) or ClinicalTrials.org (<http://www.clinicaltrials.gov>) or other local registries. Hospital del Mar researchers will review this protocol and submit the information necessary to fulfill these requirements. Information posted will allow subjects to identify potentially appropriate trials for their disease conditions and pursue participation by calling a central contact number for further information on appropriate trial locations and trial site contact information.

By signing this protocol, the investigator acknowledges that the statutory obligations under EMA clinical trials directive or other locally mandated registries are that of the investigators and agrees not to submit any information about this trial or its results to those registries.

10.5 Quality Management System

By signing this protocol, the principal investigator agrees to be responsible for implementing and maintaining a quality management system with written development procedures and functional area standard operating procedures (SOPs) to ensure that trials are conducted and data are generated, documented, and reported in compliance with the protocol, accepted standards of Good Clinical Practice, and all applicable federal, state, and local laws, rules and regulations relating to the conduct of the clinical trial.

10.6 Data Management

The investigator or qualified designee is responsible for recording and verifying the accuracy of subject data. By signing this protocol, the investigator acknowledges that his/her electronic signature is the legally binding equivalent of a written signature. By entering his/her electronic signature, the investigator confirms that all recorded data have been verified as accurate. Detailed information regarding Data Management procedures for this protocol will be provided separately.

10.7 Publications

This trial may be intended for publication, even if terminated prematurely. Publication may include any or all the following: posting of a synopsis online, abstract and/or presentation at a scientific conference, or publication of a full manuscript. The principal investigator will work with the authors to submit a manuscript describing trial results within 12 months after the last data become available, which may take up to several months after the last subject visit in some cases such as vaccine trials. Hospital del Mar researchers will post a synopsis of trial results for approved products on EUDRA or Clinicaltrials.gov by 12 months after the last subject's last visit for the primary outcome, 12 months after the decision to discontinue development, or product marketing (dispensed, administered, delivered, or promoted), whichever is later.

These timelines may be extended for products that are not yet marketed, if additional time is needed for analysis, to protect intellectual property, or to comply with confidentiality agreements with other parties. Authors of the primary results manuscript will be provided the complete results from the Clinical Study Report, subject to the confidentiality agreement. When a manuscript is submitted to a biomedical journal, the policy is to also include the protocol and statistical analysis plan to facilitate the peer and editorial review of the manuscript. If the manuscript is subsequently accepted for publication, the researchers will allow the journal, if it so desires, to post on its website the key sections of the protocol that are relevant to evaluating the trial, specifically those sections describing the trial objectives and hypotheses, the subject inclusion and exclusion criteria, the trial design and procedures, the efficacy and safety measures, the statistical analysis plan, and any amendments relating to those sections.

Authorship credit should be based on 1) substantial contributions to conception and design, or acquisition of data, or analysis and interpretation of data; 2) drafting the article or revising it critically for important intellectual content; and 3) final approval of the version to be published. Authors must meet conditions 1, 2 and 3. Significant contributions to trial execution may also be considered to determine authorship if contributions have also been made to all three of the preceding authorship criteria. Although publication planning may begin before conducting the trial, final decisions on authorship and the order of authors' names will be made based on participation and actual contributions to the trial and writing, as discussed above. The first author is responsible for defending the integrity of the data, method(s) of data analysis and the scientific content of the manuscript.

